6.5. Safety Assessments

Criteria specified in this section will be used to define, evaluate, and report subject safety during the course of their participation in the study. This NSR study will be conducted under safety reporting requirements found in 21 CFR 812.150(a)(1) and 21 CFR 812.150(b)(1).

6.5.1 Defining, Recording and Reporting Events

6.5.1.1 Adverse Event (AE)

An AE is defined as any untoward medical occurrence in a subject. This means any clinically adverse sign, symptom, syndrome or illness that occurs or worsens during the course of the study, regardless of causality, that is not otherwise being measured in the study.

Each AE will be evaluated for its seriousness, severity and association with the Imagio study. Adverse events will be followed until resolution or for the duration of the study.

6.5.1.2 Serious Adverse Event (SAE)

The severity of AEs will be assessed according to the International Organization for Standardization (ISO) 14155-1 SAE definition. A device-related SAE will be defined as an SAE in which the Imagio device relationship cannot be ruled out.

An AE that meets any of the following criteria will be considered an SAE for protocol purposes:

- 1. Led to death
- 2. Led to a serious deterioration in the health of the subject that:
 - Resulted in a life-threatening illness or injury;
 - Resulted in permanent impairment of a body structure or a body function;
 - Required in-subject hospitalization or prolongation of an existing hospitalization; or,
 - Resulted in medical or surgical intervention to prevent permanent impairment of a body structure or a body function.
 - Resulted in persistent or significant disability or incapacity; or
 - Important AEs that are not immediately life-threatening or do not result in death or
 hospitalization but, based on the training physician's medical judgment, may jeopardize
 the subject or may require intervention to prevent one of the other outcomes listed
 above.

Neither a biopsy nor a diagnosis of breast cancer is considered to be an adverse event.

6.5.1.3 Unanticipated Adverse Device Effect (UADE)

As defined by FDA regulation at 21 CFR 812.3(s):

Unanticipated adverse device effect means any serious adverse effect on health or safety or any life-threatening problem or death caused by, or associated with, a device, if that effect, problem, or death was not previously identified in nature, severity, or degree of incidence in the investigational plan or application (including a supplementary plan or application), or any other unanticipated serious problem associated with a device that relates to the rights, safety, or welfare of subjects.

An observer in this study must report any suspected UADE to the Seno Medical Director within 24 hours of learning of the occurrence. Seno will then report any concerned UADEs, as required by FDA regulations.

6.5.2 Evaluation of Severity

The severity of AEs will be assessed according to the following definitions:

Mild: The AE is noticeable to the subject but does not interfere with routine activity. The AE does not require any action in connection with the study treatment.

Moderate: The AE interferes with routine activity, but responds to symptomatic therapy or rest. The AE may require action concerning the study treatment.

Severe: The AE significantly limits the subject's ability to perform routine activities despite symptomatic therapy. The AE may require action concerning the study treatment.

Life-Threatening: The AE is of a nature that the subject is at immediate risk of death, even if not related to the study treatment. The AE may require action concerning the study treatment.

6.5.3 Evaluation of AE Relationship to Investigational Device

The relationship between an AE and the study device (investigational device) will be determined by the investigator on the basis of his or her clinical judgment and the following definitions:

Table 4: Evaluation of AE Relationship to Investigational Device

Likely related	AEs with clear temporal and/or spatial relationship to study device, with no clear alternative underlying cause.
Probably related	AEs with reasonable temporal and/or spatial relationship to study device that cannot be readily explained by the subject's clinical state or other agents/therapies.
Possibly related	AEs with fair temporal and/or spatial relationship to study device, with no clear alternative underlying cause.

Seno Clinical Study Protocol: PIONEER-01 300176 Rev 8 PIONEER 01 Protocol Amendment 3.2

Not related	AEs that do NOT follow a temporal and/or spatial relationship to study
	device and can be readily explained by an alternative cause, such as an
	accidental injury or expected progression of an underlying or concomitant
	disease.

6.5.4 Reporting of Adverse Events

After the informed consent has been obtained, the investigator, or designee, will determine whether any AEs have occurred. Any AEs will be reported in the subject's medical record and on the AE CRF page, and each will be classified according to the aforementioned criteria.

The following categories of adverse events will be entered onto the eCRF:

- 1. Any adverse events related to the breast in which the lesion(s) is identified
- 2. Any procedure-related adverse events including adverse events associated with mammography, conventional diagnostic ultrasound, Imagio, or biopsy.

Any pre-existing conditions that are detected as part of the Enrollment procedures must be reported in the medical history and not as an AE. Regulatory reporting standards will be followed for qualifying serious or unexpected events as per 21 CFR 812.

As part of the safety evaluation, all AEs need to be captured in study records for analysis and inclusion of the analysis/findings in the study report. This includes following all AEs through resolution or study completion to assure subject well-being, safety and rights.

6.5.5 Serious Adverse Event (SAE) and Unanticipated Adverse Device Effect (UADE)

All SAEs and UADEs must be reported from the time the subject signs the informed consent form (ICF) through their study duration.

The investigator, or designee, must report all SAEs and all UADEs to the sponsor or sponsor's authorized representative within 24 hours of notification of the event. The completed SAE form must be sent to the study contact noted below:

[name] Medical Director Seno Medical Instruments, Inc. [contact]

[contact]

Necessary SAE forms will be provided to the investigator. If the event has been classified as a SAE or UADE, details of medical history, concomitant medications and an evaluation of compliance with study

Seno Clinical Study Protocol: PIONEER-01 300176 Rev 8 PIONEER 01 Protocol Amendment 3.2

Confidential Page 47 of 80

evaluation should accompany the form. The investigator, or designee, must also report the resolution of reported SAEs/UADEs promptly.

The investigator will report all SAEs and UADEs to his/her IRB as per the IRB guidelines.

All SAE and UADE collection forms will be provided as part of the site files and placed within the site's regulatory binder as will be the appropriate contact information for safety reporting.

6.5.6 Reporting and Recording Adverse Events (AEs)

As part of the safety evaluation, all AEs need to be captured in study records for analysis and inclusion of the analysis/findings in the study report. This includes following all AEs through resolution or study completion to assure subject well-being, safety and rights.

The investigator, or designee must complete the UADE form and notify the sponsor or sponsor's authorized representative within 24 hours. The investigator will report all AEs and UADEs to his/her IRB, as per the IRB guidelines.

6.6 Removal of Subjects from the Study

The investigator may withdraw a subject from this study to promote subject safety and/or due to protocol non-compliance.

6.7 Appropriateness of Measurements

Imagio was developed to complement and to add additional knowledge to existing imaging modalities. The selected endpoints (sensitivity, specificity, concordance (percent TP and TN), positive likelihood ratio (Se/ (1-Sp)), negative likelihood ratio (Sp/ (1-Se)), NPV and PPV), and odds ratio give an adequate characterization of the Imagio System in the indications for use by:

- Decreasing the number (percent) of women potentially undergoing biopsy by identifying those unlikely to have a malignant mass while not increasing the number (percent) of false-negative to a clinically unacceptable level (see Non-Inferiority margin discussion).
- Showing that Imagio has a sufficiently high specificity relative to the Imagio ultrasound component.
- Showing that Imagio features differentiate between benign and cancer cases.
- Down classifying BI-RADS 3, 4a, and 4b subjects according to the site investigator.
- Down classifying BI-RADS 3, 4a, and 4b subjects according to IUS.
- Up classifying BI-RADS 3, 4a, and 4b subjects according to IUS

7. QUALITY CONTROL AND ASSURANCE

Seno or its designated representatives performs at least monthly quality assurance checks on all investigational devices at participating sites. Phantoms and testing protocols will be supplied. The

Seno Clinical Study Protocol: PIONEER-01 300176 Rev 8 PIONEER 01 Protocol Amendment 3.2

investigational devices will be delivered and installed by Seno. Seno will provide guidance on the daily operation, back-up, and maintenance of all investigational devices including data transfer.

A Truth Panel will consist of two independent expert radiologists and a histopathologist; the Truth Panel will work closely with the Sponsor and/or designee to adjudicate all cases and to review anomalies relating to pathology, imaging, subject history, and clinical course for the additional purpose of alerts regarding subjects at risk for malignancy, but not biopsied.

• Quality Control and Assurance are conducted by the core imaging lab. A QA evaluator who is a QA radiologist (QAR) (separate from the independent reviewers) will perform an image/lesion pairing assessment once the ICC performs the QA of all demographic data, checks image completeness and quality, and resolves all discrepancies. The ICC must perform this QA before the independent review can take place. The QARs will also check if lesions scanned with Imagio at the site match the same lesion(s) seen on all imaging modalities at the site. The QA Radiologists review and select the relevant images and videos to allow unbiased and least burdensome IR review and ensure the imaging data can be read consistently, without ambiguity. In addition, criteria are in place to identify unbiopsied cases with a risk of malignancy according to the independent registration readers.

For the Pivotal Study component, subsets of 5% of registration image sets and 2.5% of all reimbursement image sets will be reread to assess learning and consistency.

In addition, Seno or its designated representatives will monitor all clinical studies that it sponsors. Before the enrollment of subjects in this study, the sponsor or sponsor's authorized representative and the investigator will review the protocol, the eCRF and instructions for completing them, the procedure for obtaining informed consent and the procedure for reporting AEs/UADEs/SAEs. Site monitoring visits will be performed by the sponsor or sponsor's authorized representatives on a regular basis. During these visits, information recorded in the eCRFs will be verified against source documents. The eCRF will be reviewed for device performance and compliance issues, safety information, legibility, completeness, accuracy and logical consistency. The data will reside in an electronic database. Additional computer programs that identify selected protocol violations, out-of-range data and other data errors may be used to help monitor the study. As necessary, requests for clarification or correction will be sent to the investigator.

Independent auditors from the sponsor or sponsor's authorized representative will be allowed by the investigator to audit previously monitored data. In addition, audits may be conducted by appropriate regulatory authorities.

Data entered in the eCRF will be source verified for accuracy and completeness. In addition, protocol compliance and compliance with FDA and EU regulations, including GCP, ICH, and ISO requirements, will be verified.

8. STATISTICAL METHODS

8.1 General Considerations

8.1.1 Statistical Strategy

This is a MRMC design involving two image sets (Imagio and its' ultrasound component) for registration (according to 7 independent readers) and multiple combinations of image sets for reimbursement (according to 3 other independent readers). The registration readers will review all cases while the reimbursement readers will read multiple combinations of image sets. The PMA filing will be based on the registration results with the reimbursement results to be submitted at a later date.

A total of at least 1700 women at 16 US sites are planned to undergo an Imagio evaluation following prospective enrollment, provided there are a sufficient number of benign masses (at least 1,000 masses) and, if there is not a sufficient number, then the total number of subjects will increase to achieve at least 1,000 benign masses. Subjects with an undiagnosed suspicious finding within the previous 45 business days, by palpation or by a screening or diagnostic methodology other than ultrasound, and scheduled to undergo a conventional diagnostic ultrasound will be prospectively screened. Subjects with only a BI-RADS 1 or BI-RADS 2 classification will be regarded as screen failures. This strategy reduces referral bias and accounts for a consecutive series of BI-RADS 3 and BI RADS 4 cases not discovered according to CDU. Once a decision has been made to biopsy (yes or no), the subject will then undergo an Imagio evaluation of all masses to be biopsied (up to a total of three per subject from both breasts). The Imagio results will not be used to decide whether or where to biopsy or to reverse the decision to biopsy; also no study-related follow-up is planned after the biopsy.

The analyses will be performed at the mass level since some subjects will have more than one mass biopsied. It is expected that no more than 5% of all subjects will have multiple masses so no repeated measures analyses are planned, that is, all lesions will be treated as independent observations.

Subjects will be drawn from the following four subpopulations selected by the site investigator to undergo diagnostic ultrasound and then Imagio:

- Callbacks for additional evaluation of suspicious area(s) identified by imaging other than ultrasound.
- Diagnostic referral to assess focal physical symptoms and / or signs that were either a chief complaint of the subject or were elicited by the healthcare practitioner (excluding focal breast pain in the absence of other positive clinical findings).
- Interval Clinical Problems (symptoms or physical findings excluding isolated focal breast pain, that have developed between yearly mammograms).
- Other referrals to diagnostic conventional ultrasound including subjects younger than 30 years old for a clinically suspicious area, or subjects referred from a screening MRI because of an

abnormality.

These subpopulations will be analyzed in aggregate as well as individually.

The Imagio diagnostic ultrasound component will serve as the "internal control".

The specificity determined by a 2% POM is the primary effectiveness endpoint while the sensitivity is the secondary effectiveness endpoint.

Multiple effectiveness endpoints will be assessed (one primary and four secondary) so the overall 5% Type I error will be controlled by requiring two-sided p=0.01 to establish statistical significance. Specificity will be tested first according to a superiority test while sensitivity will then be tested according to non-inferiority tests. Testing will be based on the specificity (primary endpoint) and sensitivity (secondary endpoint), both based on a 2% Probability of Malignancy (POM). The overall specificity exceeding 40% will also be tested. In addition, downgrading benign masses and upgrading malignant masses using Imagio relative to the site and relative to IUS will be evaluated.

The superiority test and the non-inferiority tests will each have at least 80% power to test their respective hypotheses according to a two-sided test with overall 1% Type I error. The histopathology findings of the biopsy procedure will serve as a gold standard for Imagio. The decision to not recommend a biopsy during the first 12 months together with a negative 12 month clinical and imaging follow-up and no evidence of a >20% increase in the mass will be regarded as evidence of no disease (True-Negative for a negative OA/FN for a positive screening OA) for those initially not recommended for biopsy.

A total of 7 independent radiologists will be assigned per each case to independently evaluate both image sets (IUS and Imagio) per subject. In addition, 3 other independent readers will perform the reimbursement reads. All independent readers will evaluate all Pivotal Study cases; the readers will also review 5% of all cases to assess temporal trends and consistency; the initial evaluation will be used in all analyses.

Each registration reader will review the data from the two image sets (IUS, Imagio) for each case; each reader will evaluate Imagio according to a pre-determined diagnostic rule set based on OA image characteristics and will similarly evaluate IUS according to another pre-determined diagnostic rule set and each reader will estimate the probability that the mass is cancer on a scale from 0% to 100% in 5% increments (1% if \leq 10% or \geq 90%). Readers will assess IUS and Imagio in this pre-defined order during independent review sessions; this pre-defined order is consistent with medical practice.

Registration readers will also have access to the results of two locked nomograms to separately predict the POM and the probability of cancer. These nomograms were constructed from the Pilot Study cases using a linear model for the POM and a logistic regression model for the probability of cancer. The nomograms are constructed from the five feature scores for Imagio from a blinded review performed by [name]. The registration readers do not need to use the results of the nomograms in making their POM judgments, but they will immediately see the two predictions as soon as they score the five

features. The sensitivity and specificity of the nomograms will also be evaluated using the average predicted score; if the average is ≤ 0.1 , then the case is predicted to be benign.

The final sample size of the Pivotal Study will be determined by an interim analysis after the first 800 Pivotal Study subjects (cases 101-900 passing Quality Assurance review) have been evaluated with Imagio plus the results of any pre-scheduled biopsies; the final sample size will depend on the numbers of masses biopsied, the percent of biopsied masses with a cancer diagnosis, and the sensitivities and specificities for Imagio and IUS among biopsied masses. The interim analysis will be conducted once at least four of the seven registration readers complete the review of the 800 cases. Results will be shared with partners for business planning purposes based on all 7 registration readers but will not be shared with sites or published until the study is completed. The final sample size will not exceed 2,400 masses.

The study design will require all images to be managed by an independent ICC according to FDA guidelines (FDA Clinical Performance Evaluation: Considerations for Computer-Assisted Detection Devices Applied to Radiology Images and Radiology Device Data – Pre-market Approval [PMA] and Pre-market Notification [510k] Submissions, October 21, 2009). The ICC will assign multiple readers per team to review all images leading to the decision to either perform a biopsy or to follow the subject for up to 12 months. To best replicate clinical relevance where mammography and conventional diagnostic ultrasound will be read first in practice, the image sets will be read in the following order:

- 1. Imagio diagnostic ultrasound alone
- 2. Imagio (diagnostic ultrasound plus opto-acoustics).

To preserve their independence and objectivity as well as to minimize bias, the independent readers must lock their IUS evaluations before being allowed to begin their Imagio evaluations; in addition, readers will NOT have access to any clinical data but will have access to biopsy outcomes once they record and lock their evaluations. Then readers will have controlled access to biopsy outcomes in units of 25 cases to simulate the real world setting where practicing radiologists receive outcomes.

Variable referral patterns across sites are expected. The referral pattern also varies depending on study site (academic vs. private practice), age, risk factors (family history of breast cancer, obesity), and breast BI-RADS density. Note that pre-screening and referral patterns influence diagnostic performance, helping to explain a breast cancer detection rate (BCDR) ranging between 18% and 40%. Endpoints of family history of breast cancer and obesity were not collected in this study.

The histologic findings of the biopsy procedure will serve as a gold standard for Imagio and the decision to not recommend a biopsy during the first 12 months will be regarded as evidence no of disease (True-Negative) for those not recommended for biopsy. Images will be assessed according to if the biopsy was performed immediately, delayed, or irrespective of timing through the 12 month follow-up interval.

High risk histologies will be analyzed separately from benign and malignant histologies in all data analyses. This reflects current practices where high risk masses are considered to be benign histologies but are always removed.

In general, superiority will be assessed using a two-sided 99% lower bound \geq 0 while non-inferiority will be assessed using a one-sided 99.5% lower bound greater than or equal to the non-inferiority margin.

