8.2 Study Hypotheses

The above considerations motivate multiple hypotheses. As pre-specified below, Hypothesis 1 tests Imagio specificity superiority versus IUS (H1) while Hypothesis 2 tests Imagio sensitivity non-inferiority versus IUS (H2). Hypotheses 3 and 4 test if the stand alone Imagio specificity is at least 40% (H3) and the stand alone sensitivity is at least 90% (H4). Hypothesis 5 tests the hypotheses for using Imagio to downgrade benign masses to BI-RADS 2 and 3 from BI-RADS 3, 4a, and 4b using IUS (H5) and upgrade malignant masses relative to IUS (H6).

The study hypotheses are as follows:

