8.2.4. Hypothesis 4: Imagio has acceptable stand-alone sensitivity

Null hypothesis) H_0 : Sensitivity = 90%

versus

Alternative hypothesis) Ha: Sensitivity > 90%

A stand-alone sensitivity exceeding 95% is regarded as being clinically meaningful.

8.2.5. Hypothesis 5: Imagio evaluation improves the overall diagnostic efficiency for benign masses as measured by the relative risk in the BI-RADS 3 and BI RADS 4a and BI RADS 4b subgroups according to IUS. A reduction of BI-RADS 4a and BI-RADS 4b according to IUS to BI-RADS 2 or 3 according to Imagio would be a major advance as would a reduction of BI-RADS 3 according to IUS to BI-RADS 1 or 2 according to Imagio. Specifically, the cancer prevalence ranges from 2% to 10% for the BI-RADS 4a category and 11% to 50% for the BI-RADS 4b category so a reduction to 1% or 2% would be equivalent to BI-RADS 2 or 3 which would be sufficient to prevent negative biopsies and to delay interval follow-up. A similar benefit would be to reduce cancer prevalence from 2% to <2% for the BI-RADS 3 subgroup.

Null hypothesis) H_o: No difference in BI-RADS according to Imagio vs. IUS

versus

Alternative hypothesis) H_a: Decreased BI-RADS according to Imagio vs. IUS

A 25% reduction to BI-RADS 2/3 from BI-RADS 3/4a/4b is regarded as being clinically meaningful for benign masses.

8.2.6. Hypothesis 6: Imagio evaluation improves the overall diagnostic efficiency for malignant masses as measured by the relative risk in the BI-RADS subgroups according to IUS. An increase in BI-RADS according to IUS to higher BI-RADS according to Imagio would be a major advance.

Null hypothesis) H_o: No difference BI-RADS according to Imagio vs. IUS

versus

Alternative hypothesis) H_a: Increased BI-RADS according to Imagio vs. IUS

A 10% increase in BI-RADS 3/4a/4b/4c to higher BI-RADS 4c/5 is regarded as being clinically meaningful for malignant masses.

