8.6. Sample Size Calculations

The sample size calculations for the Pivotal Study may be increased based on the n=800 interim analysis results. The Pilot Study results will solely be used to validate the algorithm and will not count towards the Pivotal Study sample size.

The interim analysis will provide key information to check the preliminary assumptions regarding the degree of correlations between Imagio and IUS. Imagio can theoretically succeed with improvements relative to the above two diagnostic gray scale citations (25, 26) with success

optimized if Imagio can rule out suspicious benign cases (minimizing the false-positive percents). The following table summarizes the specificity superiority tests to detect a conservative absolute 6% advantage which can be performed with 90% power for 860 benign masses assuming 20% discordant.

Table 6: 99.5% Superiority: McNemar's test (Specificity Difference: Paired Proportions

	1
Test significance level, $lpha$	0.5%
Expected difference, $\delta = \pi_1 - \pi_2 $	6%
Proportion discordant, $\eta = \pi_{10} + \pi_{01}$	20%
Power (%)	90
n (number of pairs)	860

The following table summarizes the sensitivity non-inferiority margin (5%) which can be ruled out with 90% power for 420 cancer masses.

Table 7: 99.5% Non-inferiority Confidence Bound: Sensitivity Difference: Paired Proportions (simulation)

	1
Confidence level, 1- $lpha$ (one-sided)	99.5%
Expected difference, π_{T} - π_{S} , Δ_{1}	0%
Proportion discordant, $\eta = \pi_{10} + \pi_{01}$	5%
Proportion both yes, π_{11}	94%
Lower limit for π_T - π_S , LL	-5%
Power (%)	90
n (number of pairs)	420

The following table displays the threshold needed to reject the null hypothesis of 40% specificity with 80% power according to a 99.5% lower bound for 1,160 benign masses. An observed 45% specificity would reject the 40% null hypothesis.

Table 8: 99.5% Exact Lower Bound: Specificity

	1
Test significance level, 1- α	99.5%
Null hypothesis proportion,	π_0 40%
Alternative proportion, π_A	45%
Power (%)	80
N	1160

Seno Clinical Study Protocol: PIONEER-01
300176 Rev 8 PIONEER 01 Protocol Amendment 3.2

The following table displays the threshold needed to reject the null hypothesis of 90% sensitivity with 80% power according to a 99.5% lower bound for 360 cancer masses. An observed 95% sensitivity would reject the 90% null hypothesis.

Table 9: 99.5% Exact Lower Bound: Sensitivity

	1
Test significance level, 1- α	99.5%
Null hypothesis proportion, π_0	90%

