8.7. Analyses

8.7.1 Sensitivity and Specificity

The specificity for Imagio relative to the Imagio ultrasound component (IUS) will be assessed using a one-sided 99.5% lower confidence bound. The goal is to establish at least a 6% absolute advantage in specificity for Imagio vs IUS.

Seno Clinical Study Protocol: PIONEER-01
300176 Rev 8 PIONEER 01 Protocol Amendment 3.2

The sensitivities and specificities will be displayed for Imagio relative to IUS; in these displays, the consequences of Imagio (positive vs. negative) will be considered and compared using a generalized linear model (GENMOD) to account for correlated outcomes among the readers.. Additional analyses will be performed using the nomograms for the POM and the diagnosis based on the five Imagio features. The first nomogram models the probability of malignancy (NPP) while the second nomogram models the probability of cancer (NPC). The sensitivity and specificity of the averaged prediction (NPP and NPC) being ≥ 0.1 or ≤ 0.1 will be evaluated. The ability of the nomogram to downgrade benign masses with IUS POM $\leq 30\%$ and CDU POM $\leq 30\%$ will also be assessed. The linear regression (NPP) and the logistic regression (NPC) models behind the predictions are based solely upon the Pilot Study data.

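### The two-sided 0.01 level splits 5% over five endpoints, but section 8.2 states six hypotheses, so overall 5% control is not guaranteed as written

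*Protocol*

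**What the plan says.** Section 8.1.1 derives the level from a count of endpoints: "one primary and four secondary) so the overall 5% Type I error will be controlled by requiring two-sided p=0.01 to establish statistical significance". The tests it then names number five: specificity superiority, sensitivity non-inferiority, specificity above 40%, downgrading of benign masses and upgrading of malignant masses. On sequence it says only: "Specificity will be tested first according to a superiority test while sensitivity will then be tested according to non-inferiority tests".

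Section 8.2 lists six hypotheses. Its introduction runs the last two together under Hypothesis 5 ("using IUS (H5) and upgrade malignant masses relative to IUS (H6"), but section 8.2.6 gives the sixth its own heading, null and alternative: "Hypothesis 6: Imagio evaluation improves the overall diagnostic efficiency for malignant masses". Section 8.2.4 is a further formal test, "Hypothesis 4: Imagio has acceptable stand-alone sensitivity". Section 8.1.1 does not name it, yet section 8.6 sizes it in Table 9 to "reject the null hypothesis of 90% sensitivity with 80% power according to a 99.5% lower bound for 360 cancer masses".

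The decision rules work on one side. In section 8.1.1, "non-inferiority will be assessed using a one-sided 99.5% lower bound greater than or equal to the non-inferiority margin". In section 8.7.1, the specificity comparison "will be assessed using a one-sided 99.5% lower confidence bound".

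**The concern.** The claim of overall 5% control rests entirely on there being five tests. The next section contradicts that count, and nothing else in the text restores the claim. The stated order of H1 and H2 could have been meant as a gate, but the protocol does not say that a failed H1 stops testing, and it gives H3 to H6 no order at all.

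This sentence sets the level for the registration hypotheses on which the PMA filing is based. If it stands, a secondary claim could be presented as covered by 5% control that the protocol's own hypotheses do not deliver. Section 9.12 requires the analysis plan to follow the protocol's statistical section, so the wrong count would carry over.

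**Working it through.** **Inputs.** Overall error 5%, per-test level two-sided 0.01, five endpoints (section 8.1.1); six hypotheses (section 8.2); one-sided 99.5% bounds, that is 0.5% per test in the direction of success (sections 8.1.1 and 8.7.1, Tables 6 to 9). The comparisons relative to the site are not counted: section 8.1.1 says they will be evaluated, and they are not among H1 to H6.

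**The plan's own figure.** 5 × 0.01 = 5.0%. This reproduces.

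**Six tests, no gate.** The bound is m × α; under independence the rate is 1 − (1 − α)^m.

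| | Five tests | Six tests |
|---|---|---|
| Two-sided, bound | 5 × 0.01 = 5.0% | 6 × 0.01 = 6.0% |
| Two-sided, independent | 1 − 0.99^5 = 4.90% | 1 − 0.99^6 = 5.85% |
| False success only, bound | 5 × 0.005 = 2.5% | 6 × 0.005 = 3.0% |
| False success only, independent | 1 − 0.995^5 = 2.48% | 1 − 0.995^6 = 2.96% |

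**Effect of correlation.** H1, H3 and H5 use the benign masses; H2, H4 and H6 use the cancers. The protocol gives no correlations between these tests, so I assume normal test statistics, all six nulls at their boundary, a common correlation within each group and none between groups.

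| Correlation | Two-sided, six tests | False success only, six tests |
|---|---|---|
| 0 | 5.85% | 2.96% |
| 0.3 | 5.70% | 2.87% |
| 0.5 | 5.38% | 2.71% |
| 0.6 | 5.12% | 2.58% |
| 0.7 | 4.78% | 2.40% |
| 0.8 | 4.31% | 2.17% |

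**Gate H2 on H1 only.** If the H1 null is true, a false rejection of H2 requires a false rejection of H1, so the pair costs at most 0.01. H3 to H6 add 4 × 0.01, giving 0.05. If the H1 null is false, only H2 to H6 can be falsely rejected: 5 × 0.01 = 0.05. The bound is 5.0% either way.

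**Gate H2 to H6 on H1.** The bound is max(0.01, 5 × 0.01) = 5.0%.

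**Bonferroni over six.** 0.05/6 = 0.00833 two-sided, or 0.00417 one-sided. Power at the protocol's sample sizes:

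| Test | At one-sided 0.005 | At one-sided 0.00417 |
|---|---|---|
| H1, McNemar, 6% difference, 20% discordant, 860 pairs: normal approximation | 91.5% | 90.5% |
| H1, continuity-corrected | 90.2% | 89.1% |
| H1, exact conditional | 90.8% | 89.8% |
| H3, exact binomial, 40% vs 45%, n = 1,160 | 80.4% (critical count 508) | 78.7% (509) |
| H4, exact binomial, 90% vs 95%, n = 360 | 80.4% (critical count 339) | 80.4% (339) |

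The normal-approximation entries use Φ[(d√n − z√η)/√(η − d²)] with d = 0.06, η = 0.20 and n = 860. The first column agrees with the 90%, 80% and 80% stated in Tables 6, 8 and 9, which confirms that each test was planned at one-sided 0.5%.

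**The case against.** Four points can be made for the plan.

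- **The six nulls may not all be able to hold.** The H6 null is no difference in BI-RADS for malignant masses. Read as exact equality, it implies equal sensitivity at the 2% cut, so the H2 null of a loss of at least 5 points would be false. At most five nulls could then be true, and the bound would be 5.0% without a gate. This holds only under that reading. The H6 alternative is directional, and section 8.7.5 compares discordant pairs by McNemar's test. Upgrades and downgrades can balance while enough cancers fall below the 2% cut to cost 5 points of sensitivity, so both nulls can be true together.
- **Success is judged on one side.** The chance of a false success is at most 3.0%, which is below 5%. That is correct and limits the practical harm. But section 8.1.1 makes its claim for two-sided 0.01, and on that scale six tests do not sum to 5%. The 2.5% comparator is the same five-test accounting taken in one direction; the protocol does not state it.
- **The order of H1 and H2 can be read as a gate.** If it is one, the bound is 5.0%. But the text names no consequence of a failed H1, and it justifies the 5% by the number of endpoints rather than by sequence.
- **The division is right and the effect small.** 0.05/5 is indeed 0.01, and section 8.1.1's own list does come to five. The error lies in the count. With strong enough correlation the actual rate is below 5%.

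**Conclusion.** The concern holds. The protocol's 5% control does not follow from its own six hypotheses: as written, the guaranteed two-sided bound is 6.0%, and the bound on false success is 3.0% where five tests would give 2.5%. This assumes that all six hypotheses are confirmatory, that the stated order is not binding, and that the H6 null is no net increase rather than exact equality. The actual rate depends on correlations the protocol does not give and may lie below 5%.

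Which hypothesis was left out of the count is an inference. The likeliest is H4, which section 8.1.1 does not name although Table 9 sizes it; the merging of H5 and H6 in the introduction to section 8.2 is another possible source. The mismatch of five and six does not depend on the answer.

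H1 is still tested at its own 1% level. The point should be corrected, but it does not threaten the primary test.

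**What to change.** In section 8.1.1, change the count to one primary and five secondary, list H1 to H6, and turn the existing order into a rule, for example: *H2 is tested only if H1 is rejected in Imagio's favour; every test is at two-sided 0.01.* This needs no change of level, table or sample size. Its cost is that the H2 claim is lost if H1 fails. It should be written before results are known. Gating all of H2 to H6 on H1 is also valid, but then all five secondary claims are lost if H1 fails.

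The alternative is two-sided 0.05/6 = 0.0083 for every test. The 99.5% level in Tables 6 to 9 would then have to be restated, with power of about 89 to 90% in Table 6 and about 79% in Table 8. Table 9 keeps 80.4%. Table 7 rests on a simulation that would have to be rerun. The cost is about one to two points of power for H1 and H3.
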